### *1.2.2. An approach to obtain changes.*

We consider that a behavioral intervention designed to

- increase birth attendant concern about the effectiveness of routine clinical practices,
- stimulate their desire to review the effectiveness of their practice,
- provide them with skills to perform evidence-based clinical guidelines appraisal and development, and
- establish mechanisms through key hospital leaders to implement the guidelines and sustain them over time,

will increase the use of evidence-based practices in Latin American countries.

Our proposal is based on the following assumptions:

*(a) Clinical guidelines may be used to enhance the quality of care provided to patients.*

Clinical guidelines are systematically developed recommendations, used to assist patients and professionals in decisions concerning the appropriate health care for specific clinical circumstances (Duggan and Cohen, 1998).

The utilization of scientifically valid clinical guidelines can facilitate more consistent, effective, and efficient health care that would lead to improvement of the health of the population.

A review of 59 controlled trials that evaluated the effect of the implementation of clinical guidelines on the process of health care showed that in 55 of them, the implementation of the guidelines generated positive changes in the medical behavior. In 9 of 11 of these studies in which morbidity outcomes were evaluated, the outcomes improved (Grimshaw et al., 1993).

In order to achieve these results, clinical guidelines should fulfill a careful systematic process of development, implementation, and maintenance. In the last decade, this process has had a great development of its methodological aspects, mainly in developed countries that follow strong evidence-based medicine criteria for the development of its health policies.

*(b) Clinical guidelines should be developed or critically appraised and adapted by clinicians.*

For that purpose, health professionals should learn to evaluate (critically appraise) medical literature. Clinicians should regularly consult the original literature and be able to

critically appraise the methods and results sections to solve clinical problems and provide optimal patient care.

The underlying belief is that physicians can gain the skills to make independent assessments of evidence and thus evaluate the credibility of opinions being offered by experts. In general, the new skills that are needed to sustain this approach are the following: (1) identify clinically relevant problems and formulate the problems as questions that can be answered; (2) define what information is required to solve the problems; (3) conduct an efficient search of the literature; (4) select the best of relevant studies by applying the rules of evidence to determine their validity; (5) be able to present, in a succinct fashion, the content of the article and its strengths and weaknesses; and (6) extract the clinical message and apply it to the clinical problem. One of the objectives of the proposed intervention is to implement a training strategy at the hospital level to teach these skills to birth attendants and opinion leaders in order to develop simple clinical guidelines.

*(c) The strategies to be used have to be based on methods likely to be effective in changing professional behavior.*

Many methods to change medical behavior have been developed and used in industrialized countries. A comprehensive review by Oxman et al. (1995) examined 102 studies of improving physician practices and concluded that there are no "magic bullets." They conclude that the best approach is to combine several strategies, such as the use of local opinion leaders, workshops, outreach visits (academic detailing), reminders, and audit and feedback. Other, more recent, reviews showed similar conclusions (Bero et al., 1998). Similarly, Grol (1997) states that no one method of changing practices is superior. He recommends using a stages-of-change/diffusion of innovations theoretical model. The steps include (a) develop the proposal based on sound evidence and/or consensus of opinion leaders, and present the proposal to credible groups in an attractive and easily accessible format; (b) identify barriers/obstacles to change; (c) link interventions to obstacles and different phases of the change process (different interventions may be needed for different target groups of clinicians); (d) develop the plan; and (e) carry out plan and evaluate progress.

*(d) The intervention should follow a theoretical framework of stages of change.*

The intervention should be based on a multilevel theoretical framework that tailors interventions according to the stage of change of the individual practitioner and the stage of diffusion of innovations at the hospital level.

The Stages of Change Transtheoretical Model (TTM) could serve as the theoretical basis for the intervention at the level of the individual birth attendants. The TTM is a particularly useful heuristic approach for understanding how people undergo the process of changing practices and behaviors and how interventions can best be designed to promote behavioral change (Prochaska et al., 1992). At the core of the model is the assumption that behavioral change is a dynamic process that involves several distinct stages. The stages include precontemplation (not considering changing one's behavior), contemplation (thinking about changing), preparation (definitely planning to change and may have made preliminary attempts), action (has changed behavior in the short term, usually defined as within the past 6 months), and maintenance (continuing beyond 6

months) following initial change. Research in a number of health behavior areas indicates that different cognitive and behavioral factors are associated with movement through the stages (Prochaska et al., 1994). Practically, the model points to the need for different intervention strategies for individuals at different stages of the change process. For example, motivational information and confidence-enhancing messages and cues (such as chart prompts and reminders) may work best for individuals who are in the earlier contemplative stages of the process. Specific behavioral skill-training interventions and supportive normative environments, on the other hand, may be most effective for individuals in the later stages. Recent studies indicate that such tailored interventions are effective for promoting change in a variety of health behaviors (Skinner et al., 1999).

At the hospital level, the intervention should be based on the Diffusion of Innovations model and the Stage Theory of Organizational Change. Diffusion is defined as the process through which an innovation is communicated through channels over time among members of a social system (Rogers, 1983; Beyer and Trice, 1978). An innovation is an idea, practice, service, or object that is considered new by an individual or social group. According to diffusion theory, certain characteristics of innovations increase the chances that they will be widely adopted. Innovations are more likely to succeed if they are perceived as compatible with existing value systems and lifestyles. Despite the compatibility with the existing system, people tend to adopt innovations at different rates, and this phenomenon can be used to design interventions. The "early adopters" often are more highly educated and actively use information-seeking processes. Media sources (such as broadcast media, print materials, and the Internet) are effective in promoting awareness and interest in trying new things among the early adopters. Later adopters tend to be more influenced by interpersonal sources of communication, especially from respected individuals, opinion leaders, and peers, who can promote new health practices and programs among these groups (Rogers, 1983).

Research focused on organizational changes aimed at adopting innovative policies, programs, or practices shows that change typically occurs in a series of stages. The major stages include awareness, adoption, implementation, and institutionalisation (Beyer and Trice, 1978). Organizational development principles suggest that specially in the early stages, decisions regarding organizational change should be made by participation of all levels of health providers in the hospitals in identifying problems and their solutions (Sorensen et al., 1992; Strychker et al., 1997).

We developed an intervention following the previous considerations. Table 1 shows the correspondence between the theoretical models and the components of the intervention. It will use two obstetric practices (selective use of episiotomies and active management of the third stage of labor) as models for the implementation and evaluation of the experimental intervention.

**Table 1:** Correspondence between the theoretical models and the components of our intervention.

Intervention	TTM	Organizational Change
Presentation and selection of opinion leaders	Pre-contemplation	Awareness
Guidelines development	Contemplation (early adopters)	Awareness
Dissemination	Contemplation (late adopters); Preparation	Adoption
Implementation	Action	Implementation
Maintenance	Maintenance	Institutionalization

[figure not shown]
## 2. Study Design

### 2.1. Design

#### 2.1.1. General outline

To achieve the objective of the behavioral intervention to increase the use of two evidence-based birth practices (selective use of episiotomies and active management of the third stage of labor) by birth attendants, we will randomize 24 hospitals in Argentina and Uruguay into intervention and control groups. The intervention will be based on the stages of change and organizational change theories and tailored by formative research. It will include identification and training of opinion leaders who will develop evidence-based guidelines and use a multifaceted approach to disseminate, implement, and maintain the guidelines. The approach will include seminars, academic detailing, reminders, and feedback on utilization rates. The 12 hospitals in the control group will continue with their standard in-service training activities. A preparatory phase will precede the intervention phase, and both phases will last 18 months. Figure 1 summarizes the design.

**Figure 1.** Study design.

## ***2.2. Primary Hypotheses***

Our main hypothesis is that an intervention designed to motivate and facilitate health care professionals' development through the implementation and maintenance of simple evidence-based guidelines can increase the use of evidence-based practices by birth attendants at the hospital level in Argentina and Uruguay.

The main specific aim of this project is to perform a randomized controlled trial of a behavioral intervention intended to increase the use of two evidence-based birth practices, the selective use of episiotomies and active management of the third stage of labor (injection 10 IU of oxytocin). We will randomize 24 hospitals in Department of Montevideo, Uruguay, the Province of Buenos Aires, Argentina, and the City of Rosario, Argentina.

The *main research questions* to test the main hypothesis are the following:

- Does the proposed intervention decrease the frequency of episiotomies (primary outcome) and of perineal sutures (secondary outcome) in the intervention hospitals relative to the control hospitals?
- Does the proposed intervention increase the frequency of injections of oxytocin during the third stage of labor (primary outcome), and decrease the frequency of postpartum hemorrhages (secondary outcome) in the intervention hospitals relative to the control hospitals?

*Secondary research questions* are the following:

- Does the proposed intervention increase the readiness to change of birth attendants (secondary outcome) in the intervention hospitals relative to the control hospitals?
- Are the effects, if any, sustained 1 year after the end of the intervention?

Our *other aims* are to do the following:

Facilitate capacity building within the Latin American Center for Perinatology (CLAP: Centro Latinoamericano de Perinatología) and among its network of hospitals, so that they may increase their ability to perform studies integrating behavioral and clinical research methods, and to perform large scale studies using state-of-the-art information technology.

Contribute to the Global Network by increasing access to a large number of Latin American hospitals that have the capacity to participate in multicentric randomized controlled trials and other clinical studies.

## ***2.3. Primary outcomes***

- Episiotomy rate among single vaginal deliveries.
- Rate of injection of 10 I.U. of oxytocin during third stage of labor in single vaginal deliveries.

## ***2.4.Secondary outcomes***

### *2.4.1. Clinical secondary outcomes*

- Perineal sutures rate among single vaginal deliveries.
- Incidence of postpartum hemorrhage >500ml among single vaginal deliveries.

Perineal sutures and hemorrhages will be studied to estimate the health impact of the intervention. Previous studies have established that selective use of episiotomy decreases the frequency of perineal sutures and that active management of the third stage of labor decreases hemorrhages. However, we will measure the effectiveness of their use in the context of our study.

### *2.4.2. Other secondary outcome*

Provider's readiness to change with respect to episiotomies and management of third stage of labor.

### **3. Study Population and Procedures**

---

#### ***3.1. Study Site and Populations***

We will recruit hospitals in two countries because recruiting 24 hospitals in Uruguay alone is not feasible. In Argentina, we will recruit hospitals in the province of Buenos Aires and the city of Rosario. In Uruguay, we will recruit hospitals in the Department of Montevideo. Buenos Aires and Rosario are geographically close to the coordinating center in Montevideo. Even though intervention and control hospitals will be in the same cities, they do not share personnel and are independent entities.

#### ***3.2. Inclusion and Exclusion Criteria***

##### *3.2.1. Inclusion criteria for hospitals*

Hospitals will be invited to participate in the study if they fulfill the following criteria:

- have an Institutional Review Board (IRB), or existing committee which could serve as such, or have an agreement with an IRB which reviews the research protocols implemented in the hospital;
- have at least 500 vaginal deliveries per year;
- do not have a explicit policy for selective episiotomy and for active management of third stage of labor; and
- consent to participate in the study.

Those preselected hospitals will perform a baseline data collection (see section 5.2). . According to the results of the analysis of the baseline data collection, hospitals will be excluded if the episiotomy rate is low or the rate of active management is high, according to the following cut-off points:

- Episiotomy rate in primiparous women with spontaneous vaginal deliveries below 70 %
- Rate of active management of third stage of labor over 15%

Because these hospitals do not have a policy for selective episiotomy or active management, it is expected that none of them will be excluded by this criteria. The sample size of the study was increased to allow for exclusions (see section 10.3).

---

1 This figure was selected based on a survey in 38 hospitals in Argentina. This study showed that the episiotomy rate was above 70% in 90% of the hospitals in the survey (Althabe et al., 2002).

2 A survey in 23 hospitals in Argentina and Uruguay showed an average rate for active management of the third stage of labor of 5%.

We interviewed the Head of the Obstetrical Department from 23 potentially eligible hospitals during the month of June 2000. Twenty-one confirmed that they were performing episiotomy routinely among primiparae, and 21 reported that expectant management during third stage of labor was the standard form of care (expectant management is defined as “a hands-free policy” during third stage of labor until the placenta is expelled: no use of uterotonics or special maneuvers).

### ***3.3. Sampling, Recruitment, and Screening Procedures***

CLAP coordination team will be responsible for the hospital selection. The hospitals’ fulfillment of selection criteria will be obtained through a survey to the Heads of the Obstetrical Departments.

Besides the selection criteria, the coordination unit will invite the hospitals to participate according to

- their participation in previous trials coordinated by CLAP;
- their participation in other trials or research activities; and
- their location.

In Appendix 1, we show the characteristics of each preselected hospital regarding the structure of the professional staff, number of deliveries, and clinical guidelines policy.

### ***3.4. Randomization Procedures***

Preselected hospitals will perform a baseline data collection. According to the results of the analysis of the baseline data collection, hospitals will be excluded from the study if the episiotomy rate in primiparous women is below 70% or the rate of active management is higher than 15% (see section 3.2). Those hospitals fulfilling the inclusion criteria will be randomized to either the intervention or the control group.

This study has a maximum of only 24 hospitals to allocate to the control or intervention group, and random allocation may not provide adequate balance in the groups (Treasure and MacRae, 1998). In addition, stratified allocation may not be feasible due to there being too few numbers to stratify by all important variables (Treasure and MacRae, 1999).

Minimization has the particular advantage that it can make small groups of units closely similar with respect to several unit characteristics (Altman et al., 2001). A randomization lists is not set up in advance. The first unit is truly randomized, but in each subsequent unit the treatment allocation is identified which would minimize the imbalance between groups (Pocock, 1983). In this trial all units (hospitals) enters the study at the same time, and all prognostic variable are known in advance. In this situation a computer algorithm can choose by random one allocation sequence among a set of sequences that minimizes the imbalance between groups. Such algorithm will be used to allocate hospitals in this study.

Minimization offers an acceptable alternative to randomization, and some have argued that it is superior. (Treasure and MacRae, 1998). Trials that use minimization are considered methodologically equivalent to randomized trials according to the Consort

Statement (Moher et al., 2001), endorsed by the BMJ, JAMA, Annals of Internal Medicine and The Lancet, among others.

There are four hospital characteristics that were selected as important prognostic variables. These are the variables that will be included in the minimization algorithm to assure balance between groups.

1. Teaching hospital with residents (Yes-No).
2. Country (Argentina-Uruguay).
3. Hospital size (less than 2000 – 2000 or more deliveries per year).
4. Region (Montevideo, Salto/Paisandu, Rosario, Buenos Aires).

The minimization algorithm will minimize the imbalance between groups, assigning more priority to variables 1 and 2. table 2 shows the values for the selected variables for all 24 pre-selected hospitals, and table 3 shows an example of one set of results of the minimization algorithm on these hospitals.

After the baseline data collection period the dataset will be analyzed by RTI. RTI will then apply the inclusion criteria to assess the eligibility of preselected hospital according to the baseline rate of episiotomy and active management. The statistician at CLAP will elaborate a computer program implementing the minimization algorithm. The source code of the algorithm will be made available in advance to RTI and UNC-CH for audit and testing. This computer program will be used by the statistician at RTI to allocate eligible hospitals to either intervention or control without participation of others. The assignment will then be communicated to CLAP. Thus, there will be a clear separation between the generator of the intervention assignment and the CLAP study coordination (Donner et al., 1998).

Table 2. Hospitals characteristics to be included in the minimization algorithm.

Hospital	Residents		Country		Size		Region	
	(1) Yes, (2) No		(1) Argentina, (2) Uruguay		(1) less than 2000, (2) 2000 or more		(1) Montevideo, (2) Salto/Paisandu, (3) Rosario, (4) Bs. Aires	
San Roque	Yes	1	Argentina	1	1500	1	Bs. Aires	4
M.V.de Martínez	Yes	1	Argentina	1	3400	2	Bs. Aires	4
Héroes de Malvinas	No	2	Argentina	1	3000	2	Bs. Aires	4
Materno Infantil	Yes	1	Argentina	1	2800	2	Bs. Aires	4
Bocalandro	No	2	Argentina	1	2200	2	Bs. Aires	4
Hosp. De Clínicas	Yes	1	Uruguay	2	1000	1	Mvdeo	1
Germani	No	2	Argentina	1	2500	2	Bs. Aires	4
Roque Saenz Peña	Yes	1	Argentina	1	1660	1	Rosario	3
Paroissien	Yes	1	Argentina	1	2800	2	Bs. Aires	4
Alejandro Korn	No	2	Argentina	1	1300	1	Bs. Aires	4
Durand	Yes	1	Argentina	1	2000	2	Bs. Aires	4
Ramon Carrillo	No	2	Argentina	1	1250	1	Bs. Aires	4
Hospital Centenario	Yes	1	Argentina	1	1300	1	Rosario	3
Equiza	No	2	Argentina	1	2800	2	Bs. Aires	4
Manuel Belgrano	Yes	1	Argentina	1	1200	1	Bs. Aires	4
San Martín	Yes	1	Argentina	1	3000	2	Bs. Aires	4
Hosp. Militar	Yes	1	Uruguay	2	1800	1	Mvdeo	1
Hospital de Paysandú	Yes	1	Uruguay	2	2100	2	Paysandú	2

---

Eva Perón	Yes	1	Argentina	1	1700	1	Rosario	3
Narciso López	Yes	1	Argentina	1	1750	1	Bs. Aires	4
Hospital Provincial	Yes	1	Argentina	1	1400	1	Rosario	3
Hospital de Salto	No	2	Uruguay	2	1000	1	Salto	2
Santa Rosa	Yes	1	Argentina	1	3000	2	Bs. Aires	4
Virgen del Carmen	Yes	1	Argentina	1	1300	1	Bs. Aires	4

Table 3. Example of one possible set of results of the minimization algorithm.

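### The allocation algorithm balances four hospital characteristics but not the baseline episiotomy rate, which the allocating centre already holds; the cost is precision and credibility, not bias

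*Protocol*

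**What the plan says.** Protocol section 3.4 chooses minimisation because, with at most 24 hospitals, simple randomisation may leave the groups unbalanced. It notes that "In this trial all units (hospitals) enters the study at the same time, and all prognostic variable are known in advance", so the program can pick at random from the set of allocations with least imbalance. It then states: "There are four hospital characteristics that were selected as important prognostic variables". They are teaching hospital with residents, country, size cut at 2000 deliveries per year, and region. Of these it says "These are the variables that will be included in the minimization algorithm to assure balance between groups", and on their weighting "The minimization algorithm will minimize the imbalance between groups, assigning more priority to variables 1 and 2".

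The same section fixes the order of events. "After the baseline data collection period the dataset will be analyzed by RTI"; then "RTI will then apply the inclusion criteria to assess the eligibility of preselected hospital according to the baseline rate of episiotomy and active management". The RTI statistician next runs the allocation program.

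Section 10.5 names a Student's t-test on mean percentages at the end of the intervention. It then names a t-test on log summary risk ratios built from baseline-to-follow-up ratios, and mixed models to explore confounding from imbalance. Section 5.2 says that Period I and Period III data both serve the primary analyses.

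**The concern.** A hospital's own earlier rate of the practice under study is the natural first candidate for a prognostic variable. Here that rate is measured in every hospital before allocation, is in the hands of the centre that allocates, and is used to decide eligibility. It is then left out of the balancing, and no reason is given. Meanwhile one of the four variables carries no separate information: in Table 2 every Montevideo and Salto/Paysandú hospital is Uruguayan, and every Rosario and Buenos Aires hospital is Argentine.

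At stake is how far apart the arms may start, by chance, on the primary outcome. A visible gap at baseline would enter the first comparison that section 10.5 names and would make the result harder to defend. It cannot be undone once hospitals are allocated.

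**Working it through.** **Inputs from the protocol.** Section 10.3: observed between-hospital SD of the episiotomy rate 11%, planning SD 15%, target 40% to 20%, SD of the oxytocin rate 5%, expected oxytocin rise 10% to 50%. Section 3.4: up to 12 hospitals per arm, and Table 2.

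**The plan's own figure.** Per arm, n = 2 × (1.96 + 0.8416)² × 15² / 20² = 2 × 7.849 × 225 / 400 = 8.8, so 9 per arm. This reproduces the 18 hospitals of section 10.3 (two-sided 0.05, normal approximation; power at 9 per arm 80.7%). The stated SDs are therefore usable.

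**Chance difference in baseline means.** SE = SD × √(2/n).

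| Rate | SD | n per arm | SE (points) | 95% range | P(>5 points) | P(>10 points) |
|---|---|---|---|---|---|---|
| Episiotomy | 11 | 12 | 4.49 | ±8.8 | 27% | 2.6% |
| Episiotomy | 15 | 12 | 6.12 | ±12.0 | 41% | 10% |
| Episiotomy | 15 | 9 | 7.07 | ±13.9 | 48% | 16% |
| Oxytocin | 5 | 12 | 2.04 | ±4.0 | 1.4% | 0% |

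These figures make no allowance for the eligibility cut-offs or for anything the four factors explain.

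**Do the four factors already help?** Minimising allocations of the Table 2 hospitals were simulated with double weight on residents and country (our assumption). If the four factors explain none of the baseline variation, the SD of the difference at SD 15 is 6.2 points and P(>5) is 43%, as in the table apart from simulation error. If they explain 40% (also an assumption), it is 4.9 points and 31%; at SD 11 it is 3.6 points and 16%.

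**Carry-over to the unadjusted t-test.** Shift = r × SE, where r is the hospital-level correlation between baseline and follow-up in the absence of an effect. The protocol gives no value. For r = 0.5 to 0.8 at SD 15 and 12 per arm: 0.5 × 6.12 = 3.1 to 0.8 × 6.12 = 4.9 points.

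**Room for the fix.** Of the 2,704,156 ways to split 24 hospitals 12/12, 122,424 reach the level of balance shown in Table 3 on all four factors. The best 5% of these on the two baseline rates is about 6,100 allocations; the best 10% is about 12,200. With rates simulated independently of the four factors, drawing from the best 5% cuts the SD of the episiotomy difference from about 6 points to 1.0 (SD 15), or from about 4.4 to 0.7 (SD 11).

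**The case against.** The protocol breaks no rule of its own: it names four factors it considers important, and a choice of balancing factors is partly preference. Chance differences between hospitals are already in the t-test's standard error and in the planning SD. With 24 hospitals rather than 18, t-test power for the 20-point target is about 88% at SD 15% and about 99% at SD 11%. All of this stands, and it is why the point concerns efficiency and credibility rather than validity.

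A reader might go further in four ways that the document does not support.

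- That the primary analysis ignores baseline. The log-ratio test in section 10.5 uses it, section 5.2 assigns Period I data to the primary analyses, and section 10.5 does not rank its two t-tests. Only the first-named test is unadjusted, and the mixed models merely explore imbalance.
- That a baseline gap passes in full into the result, or biases it. It passes in proportion to a correlation the protocol does not give, and allocation remains random, so there is no systematic bias.
- That both primary outcomes are equally exposed. For oxytocin, a chance difference of about 2 points stands against an expected rise of 40.
- That one individual both analyses the baseline data and allocates. The text places both tasks at RTI; that it is the same person is at most implied.

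The overlap of country and region is harmless in itself, since the protocol wants country to have priority. What survives is that the balancing omits a measured, available and very probably informative variable, in a section whose stated purpose is balance with few hospitals.

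**Conclusion.** The point holds as a recommendation to act on before allocation. The chance baseline difference in episiotomy rate has an SD of about 4.5 to 6.1 points with 12 hospitals per arm, and a 27% to 41% chance of exceeding 5 points. A one-SE imbalance at SD 15% would move the unadjusted end-of-intervention comparison by about 3 to 5 points of a 20-point target.

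This rests on the SDs in section 10.3, on the assumed correlation of 0.5 to 0.8, and on no narrowing by the eligibility screen (primiparous episiotomy at least 70%, active management at most 15%). Narrowing by the screen, or prediction of the baseline rate by the four factors, would make the figures smaller. That the baseline rate predicts better than the listed factors is sound inference, but no figure in the protocol shows it. The allocation variables are fixed in the protocol itself, so the balancing part cannot be left to a later analysis plan.

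**What to change.** In section 3.4, add the Period I episiotomy rate to the balancing criterion as a continuous term (standardised difference in arm means), with the Period I oxytocin rate as a lower-priority term. Draw at random from allocations that meet the four-factor balance and are also well balanced on these rates, for example the best 5% to 10%. Fix the rule in the source code that RTI and UNC-CH are to audit, before the baseline data are seen.

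In section 10.5, adjust the hospital-level comparison of end-of-intervention rates for the baseline rate. At 12 per arm and SD 15%, the residual SD is 15 × √(1 − r²): 13.0 at r = 0.5 and 9.0 at r = 0.8. Power for 20 points then rises from about 88% to about 95% and above 99%, ignoring the one degree of freedom spent.

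The cost is slightly more programming and a smaller allocation set, which still holds thousands on Table 2. If the screen removes hospitals, recount the set before fixing the percentage. No new data are needed.
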